## 2. INTRODUCTION

### 2.1 Background, Significance, and Rationale

Chronic kidney disease (CKD) is associated with hypertension and diabetes and affects 26 million US adults. African Americans (AA's) have higher risk of end stage renal disease (ESRD) necessitating maintenance dialysis or transplant than Whites. This disparity widens as kidney function declines. Additionally, AAs have the highest prevalence of hypertension (41% AA, 28% White) and the lowest rate of blood pressure (BP) control (43% AA versus 53% White). While improved BP control decreases CKD progression and reduces morbidity and mortality, BP control (defined as < 140/90 mm Hg) is only achieved in 50% of participants.

One in 7 AAs carry the Apolipoprotein L1 (*APOL1*) gene risk allele, but it is nearly absent in other populations. High-risk variants in the *APOL1* explain approximately 70% of the excess prevalence of CKD in AAs, conferring a 5 times higher risk for hypertensive CKD and a 10 times higher risk for ESRD. This risk is conferred by two variants (G1 and/or G2) in the last exon of *APOL1* with the high-risk genotype being G1/G1; G2/G2 or G1/G2. *APOL1* does not significantly increase CKD risk in hypertensive people with diabetes and normal renal function, but in hypertensive people with prevalent CKD, *APOL1* exacerbates worsening of kidney function and progression to ESRD regardless of diabetes diagnosis. Among adults with CKD, specific medications (angiotensin-converting enzyme (ACE) inhibitors or angiotensin receptor blockers (ARBs)) are recommended for participants of all ancestries, but 50% of participants do not receive these medications. Compounding this issue is the fact that providers do not include CKD on the problem list of 40% of participants with lab evidence of CKD, leading to widespread participant unawareness of CKD. Urine protein tests, essential for early diagnosis and prognosis of CKD, are missing in up to 30% of participants with CKD.

In Genetic Testing to Understand Renal Disease Disparities (GUARDD), investigators randomized participants to immediate (Intervention) versus delayed (Control) *APOL1* testing. Results were returned to participants through culturally appropriate clinical coordinators trained by genetic counselors, and to providers through low-intensity clinical decision support (CDS) (including best practice alerts (BPAs) with the test results and links to more provider information, participant education, and a generic message about the importance of blood pressure control). The study included a narrower phenotype of participants, excluding those with CKD or diabetes. GUARDD showed a statistically significant reduction in SBP at 3 months when comparing: 1) *APOL1* positives and negatives in the Intervention group (-6±18 mm Hg vs -3±18 mm Hg, p=0.008 cross-sectional at 3 months), and 2) Intervention *APOL1* positives versus overall Controls (-6±18 mmHg vs -3±18 mmHg, p=0.04 cross-sectional at 3 months). GUARDD also showed a trend towards a higher proportion of participants receiving renal disease testing at 12 months, as captured through electronic health records, when comparing: 1) *APOL1* positives and negatives in the Intervention group (29% vs 24%, p=0.10 cross-sectional at 12 months), and 2) Intervention *APOL1* positives versus overall Controls (29% vs 20%, p=0.01 cross-sectional 12 months). Participants self-reported making lifestyle changes and taking more blood pressure medicines in response to positive versus negative *APOL1* results. In addition, over 95% of participants were satisfied with the type, timing, and amount of information they received. Although participants were offered the option to speak with or meet with a genetic counselor, none chose to do so. Using stakeholder-engaged processes, there was an 11% rate of refusal, 93% 3-month retention rate, and 88% 12-month retention rate.

Several new developments highlight the importance of a broader pragmatic clinical trial (PCT). The GUARDD study was not powered to compare those with high risk genotypes (*APOL1* positives) in the Intervention group to *APOL1* positives in the Control group. New evidence since the study's inception also allows investigators to make CDS tools more robust, which may lead to greater action on the part of providers to improve hypertension management and renal disease screening. Finally, new data show that genetic differences affect the response to antihypertensive medication therapy, particularly in AAs. While pharmacogenetic (PGx) testing may help guide

initial or add-on antihypertensive therapy management for patients with hypertension, the impact of PGx testing on BP has not been studied in clinical trials among general or AA populations.

## **2.2 Aims and Objectives of the Study**

Because AAs are not routinely screened for *APOL1*, it is unknown whether participant or provider knowledge of genetic risk impacts participant care or outcomes. Accordingly, the main objective of GUARDD-US is to determine the effect of participant and provider knowledge of a positive *APOL1* status on BP, urine testing for CKD, and documented diagnosis of CKD.

The primary aim is to determine the effect of participant and provider knowledge of a positive *APOL1* status and accompanying guideline based clinical decision support (CDS) on blood pressure management on change in systolic blood pressure (SBP) from baseline to 3 months after randomization among the *APOL1* positive participants. Secondary aims are to:

1. Determine the effect of participant and provider knowledge of a positive *APOL1* status on the probability of documented CKD diagnosis.
2. Determine the effect of participant and provider knowledge of a positive *APOL1* status on the probability of receiving a urine microalbumin/creatinine testing and ACE-I/ARB prescription based on results of the urine microalbumin level.
3. Explore cost effectiveness, mediators, moderators, psychobehavioral impact of results disclosure on participants, and effects of participant and provider knowledge of *APOL1* status on provider treatment recommendations.

In addition, GUARDD-US will include a substudy to determine the effect of knowledge of genetic test results that predict efficacy of various antihypertensive medications on change in SBP from baseline to 3 months in *APOL1* negative individuals.

### **3. ENDPOINTS**

#### **3.1 Primary Endpoint**

The primary endpoint is the change in systolic blood pressure from baseline to the 3 month study visit in *APOL1* positive participants.

#### **3.2 Secondary Endpoints**

Secondary endpoints include:

1. Change in urine microalbuminuria/proteinuria orders from baseline to 6 months (Y/N)
2. Documented order of microalbuminuria/proteinuria tests by 6 months (Y/N)
3. Change in documented diagnosis for stage 3 CKD and above from baseline to 6 months (Y/N)
4. Documented diagnosis of CKD stage 3 and above by 6 months (Y/N)
5. Change in documented diagnosis for any stage CKD from baseline to 6 months (Y/N)
6. Documented diagnosis of all stages of CKD by 6 months (Y/N)

Please see Section 10.2 for the derivations of these endpoints.

#### **3.3 Pharmacogenetic (PGx) Substudy Endpoints**

[figure not shown]
The major endpoint for the PGx substudy is the change in systolic blood pressure from baseline to the 3 month study visit.

Additional exploratory endpoints and analyses for the PGx substudy will be described in a separate Statistical Analysis Plan (SAP).

#### 4. STUDY DESIGN

## 4.1 Study Arms & Design

This is a prospective, multicenter, unblinded, two arm, randomized pragmatic clinical trial (PCT) (**Figure 1**). Participants will be recruited from several recruitment sites (hereafter referred to as site) and randomized in a 1:1 ratio to immediate *APOL1* gene testing and return of results (ROR) to participant and provider (Intervention arm) versus delayed *APOL1* gene testing and ROR to participant and provider (Control arm). The main study will compare outcomes in a subset of the randomized population: *APOL1* positive participants in the Intervention arm (i.e., early knowledge of *APOL1* status) versus *APOL1* positive participants in the Control arm (i.e., delayed knowledge of *APOL1* status) (red outline in **Figure 1**). Participants that are *APOL1* negative in the Intervention and Control groups will not be included in the main study analyses.

[figure not shown]
**Figure 1.** GUARDD-US study design for sites participating in PGx.

The primary outcome of the main study is systolic blood pressure (SBP) at 3 months in Control-*APOL1* positive and Intervention-*APOL1* positive participants (red outline). The substudy outcome is SBP at 3 months in Intervention-*APOL1* positive participants (blue outline).

Negative PGx Control and PGx Intervention participants (orange outline). AA = African Americans. *APOL1* = Apolipoprotein L1. HTN = hypertension. PGx = Pharmacogenetics. ROR = Return of Results.

GUARDD-US will also include a substudy that randomizes participants in the Intervention arm who test negative for *APOL1* to PGx Intervention (i.e., immediate PGx ROR) and PGx Control (i.e., delayed PGx ROR) in a 1:1 ratio. Only participants from the PGx substudy participating sites are included in this substudy. This substudy will compare outcomes between participants in the PGx Control group and the PGx Intervention group (orange outline in **Figure 1**).

The study design for sites that are not participating in the PGx substudy is summarized in **Figure 2**.

**Figure 2.** GUARDD-US study design for sites not participating in PGx.

The primary outcome of the main study is systolic blood pressure (SBP) at 3 months in Control-*APOL1* positive and Intervention-*APOL1* positive participants (red outline). AA = African Americans. *APOL1* = Apolipoprotein L1. HTN = hypertension. ROR = Return of Results.

#### 4.2 Randomization

Eligible participants will be randomized in a 1:1 allocation to Intervention (i.e., immediate *APOL1* gene testing and ROR to participant and provider) and Control arms (delayed *APOL1* gene testing and ROR to participant and provider). Randomization will be stratified by clinical site with a random block size within site.

Participants that are randomized to receive immediate *APOL1* ROR will simultaneously be randomized to the PGx substudy intervention (i.e., immediate PGx gene testing and ROR to participant and provider) or the PGx control (delayed PGx gene testing and ROR to participant and provider) using a 1:1 allocation ratio. Participants from PGx substudy participating sites that test negative for *APOL1* will proceed into the PGx substudy under their assigned PGx treatment arms, while participants from non-participating sites of the substudy and participants that test positive for *APOL1* will be excluded from the substudy and receive delayed PGx gene testing and ROR.

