## **7.7 Data Collection from the Electronic Health Record**

Data from the local EHR will be used to determine: 1) components of the secondary endpoints (i.e., presence of CKD diagnosis codes in the 24 months prior to baseline and up to 8 months after baseline, urine tests obtained in the 24 months prior to baseline and in the 6 months after baseline), 2) events of interest (see Section 8.2), and 3) variables needed for Other Planned Analyses including Cost Effectiveness Analysis (CEA) (see Section 9.6). Sites will extract the relevant EHR data using prespecified algorithms developed centrally by the IGNITE PTN CC or using site-developed algorithms. If using the CC-developed algorithms, sites will modify the algorithm codes based on their own customized EHR system. Sites will be asked to conduct EHR data downloads after at least 25% of the participants have completed their 6 month visit, and approximately 6-12 months after the last patient is randomized. EHR results will be sent to the IGNITE PTN CC via secure data transfer and formatted for data analyses. Details of the EHR download and transfer process will be provided separately to relevant site personnel.

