## **9.4 Analysis of the Primary Endpoint**

To determine the effect of knowledge of a positive *APOL1* status on SBP, we will compare the change in SBP from baseline to 3 months of the Intervention – *APOL1* positive group to the change in SBP from baseline to 3 months of the Control - *APOL1* positive group using a two sided t-test with an overall two-sided type I error of 0.05. Participants that are *APOL1* negative in both the Intervention and Control groups will not be included. This primary analysis will be conducted according to the principle of intention-to-treat (ITT) with participants analyzed and endpoints attributed according to the treatment arm to which the participants were randomized, regardless of subsequent crossover or post-randomization medical care within the pre-specified subset of *APOL1* positive participants.

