## **9.5 Analysis of the Secondary Endpoints**

The effect of knowledge of a positive *APOL1* status on secondary endpoints [i.e., change in urine microalbuminuria/proteinuria orders from baseline to 6 months (Y/N), documented order of microalbuminuria/proteinuria tests by 6 months (Y/N), change in documented diagnosis for stage 3 CKD and above (Y/N) from baseline to 6 months, documented diagnosis of CKD stage 3 and above by 6 months (Y/N), change in documented diagnosis for any stage CKD from baseline to 6 months (Y/N), and documented diagnosis of all stages of CKD by 6 months (Y/N) ] will be compared between Intervention - *APOL1* positives and Control - *APOL1* positives with the proportion difference test.

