## **9.6 Other Planned Analyses**

Trends in SBP. In addition to the primary endpoint analysis described above, we will compare the time trends in SBP between Intervention – *APOL1* positive individuals and Control – *APOL1* positive individuals using a repeated measures mixed model. Since participants are randomized to Intervention and Control groups and not to the *APOL1* positive subgroups within Intervention and Control groups, there could be important differences in baseline characteristics between the two groups. For this reason, we will conduct covariate-adjusted repeated measures mixed models that will account for differences in baseline characteristics that differ between the Intervention – *APOL1* positive group and the Control – *APOL1* positive group. Potential baseline covariates include baseline SBP, age, sex, and baseline CKD. We will select the appropriate covariance matrix (e.g.,

compound symmetry, autoregressive, unstructured, or other covariance structure) based on the data to account for repeated measures.

CKD subset. If the data provide evidence of an overall difference in the primary outcome (change in SBP from baseline to 3 months) between Intervention – *APOL1* positive group and the Control – *APOL1* positive groups, we will further examine whether the effect of knowledge of a positive *APOL1* status on SBP differs among those with and without CKD. This subgroup analyses will involve testing for interactions between treatment arm and CKD using linear regression. Effect estimates will be carefully (conservatively) interpreted in conjunction with the formal interaction test. If the interaction is significant, we will test whether the time trends in effect of early versus delayed knowledge of a positive *APOL1* status on SBP differs among Intervention – *APOL1* positive group and the Control – *APOL1* positive groups in those with CKD at baseline using a covariate-adjusted repeated measures mixed model. Potential covariates are the same as described above. We will select the appropriate covariance matrix (e.g., compound symmetry, autoregressive, unstructured, or other covariance structure) based on the data to account for repeated measures.

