
conditioned on increasing age, CVD, and ESRD will be based on the literature. Details of the procedures for obtaining EHR data and estimates from the EHR will be provided in the MOP and SAP.

**PGx Substudy.** Analyses for the PGx substudy will compare outcomes between *APOL1* negative individuals with immediate PGx ROR (PGx Intervention) and *APOL1* negative individuals with delayed PGx ROR (PGx Control). A two sided t-test with a two-sided type I error of 0.05 will be used to evaluate differences in the change in SBP from baseline to the 3 month study visit between PGx Intervention and PGx Control groups. To evaluate time trends in SBP, we will also conduct covariate-adjusted repeated measures mixed models that will account for differences in baseline characteristics that differ between the PGx Intervention group and the PGx Control group. Potential baseline covariates are as described above. We will select the appropriate covariance matrix (e.g., compound symmetry, autoregressive, unstructured, or other covariance structure) based on the data to account for repeated measures. Additional exploratory endpoints and analyses for the PGx substudy will be described in a separate SAP.

Details of these statistical analyses along with all other exploratory analyses (e.g., mediators, moderators and psychobehavioral impact of results disclosure on participant outcomes and provider treatment recommendations, and medication adherence) will be described in the study SAP.

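### Site is the stratification factor but is not used in the primary or secondary tests, so a small amount of precision is given up

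*Combined protocol and SAP*

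**What the plan says.** The main allocation is described in 4.2: "Eligible participants will be randomized in a 1:1 allocation to Intervention" or Control, and "Randomization will be stratified by clinical site with a random block size within site". The synopsis expects about 46 to 60 sites.

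The analyses in section 9 do not return to site:

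- Primary endpoint (9.4): the two APOL1-positive groups are compared on SBP change "using a two sided t-test with an overall two-sided type I error of 0.05".
- Secondary endpoints (9.5): six binary endpoints are compared "with the proportion difference test".
- Trend models (9.6): "Potential baseline covariates include baseline SBP, age, sex, and baseline CKD". The only correlation modelled is between repeated measures on one participant. The subgroup regressions do not mention site either.
- PGx substudy (9.6): "A two sided t-test with a two-sided type I error of 0.05 will be used to evaluate differences" in SBP change, followed by mixed models with the same covariate list.

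For the PGx allocation, 4.2 says only that Intervention participants will "simultaneously be randomized to the PGx substudy intervention" or its control, 1:1. It does not say that this step is stratified.

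Section 9 gives no reason for leaving site out. Section 9.2 defers detail to a separate SAP that is not among the documents supplied.

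**The concern.** A factor important enough to stratify on is normally carried into the analysis, or its omission is explained. There is an added reason here. The main analysis uses only APOL1-positive participants, whose status is unknown at randomisation, so the site blocks do not balance them. The two analysed groups can differ in site mix by chance, and a t-test leaves any between-site variation in its error term. Section 9.6 itself recognises that the positive subgroups may differ at baseline, but it adjusts only the trend models for this, and site is not on the list.

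The documents give some ground for expecting sites to differ on the EHR endpoints, since 7.7 allows extraction by algorithms "developed centrally by the IGNITE PTN CC or using site-developed algorithms".

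What is at stake is the width of the confidence intervals and a little power in a trial sized at 80% with no slack. The validity of the tests is not at stake.

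**Working it through.** **Inputs.** From 9.1: difference 3.5 mm Hg, SD 18.1, 844 completers (422 per arm), 10% loss, 14% prevalence. From 9.7: final alpha 0.0492, so z = 1.967. From the synopsis: 46-60 sites. Assumed: the site ICC ρ (the between-site share of the variance of SBP change), taken from 0 to 0.10, and unequal site sizes.

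**1. The plan's own figure.** n per arm = 2 × 18.1² × (1.967 + 0.842)² / 3.5² = 422, so 844 in total. 844 / 0.90 = 938, and 6700 × 0.14 = 938. SE = 18.1 × √(2/422) = 1.246. Power = Φ(3.5/1.246 − 1.967) = Φ(0.842) = 80.0%. The plan reproduces exactly. It uses the full SD and takes no credit for site.

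**2. Balance within site.** 844/60 = 14 and 844/46 = 18 analysed positives per site. The arm split within a site is close to binomial.

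**3. Three estimators of the SBP difference.** Let site k contribute n1k and n0k participants to arms of total size N1 and N0, with nk = n1k + n0k.

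- t-test: variance = σ²(1−ρ)(1/N1 + 1/N0) + σ²ρ Σ(n1k/N1 − n0k/N0)².
- Random site intercept: generalised least squares variance, taking ρ as known.
- Fixed site terms: variance = σ²(1−ρ) / Σ(n1k n0k / nk).

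For the first two, averaged over simulated site sizes and binomial arm splits, the t-test SE stays at about 1.25 (1.247 at ICC 0; power about 80%) across the range. The random intercept gives:

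| ICC | SE | Power |
|---|---|---|
| 0 | 1.247 | 80.0% |
| 0.02 | 1.242 | about 80.3% |
| 0.05 | 1.229 | about 81% |
| 0.10 | 1.201 | about 83% |

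As a check, Φ(3.5/1.201 − 1.967) = Φ(0.947) = 82.8%. The ceiling, with all between-site variance removed at no cost (SD × √(1−ρ)), is 80.8%, 82.0% and 84.0% at ICC 0.02, 0.05 and 0.10.

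A separate simulation of the whole design (46 and 60 sites, blocks of 4 and 6, a random 12.6% analysed) compared the t-test with fixed site terms. Monte Carlo SE is about 0.009.

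| ICC | t-test power | Fixed-site power |
|---|---|---|
| 0 | 0.79-0.80 | 0.77-0.78 |
| 0.02 | 0.79-0.80 | 0.78-0.79 |
| 0.05 | 0.81-0.82 | 0.81 |
| 0.10 | 0.79-0.80 | 0.81-0.82 |

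**4. Type I error.** In the same simulation the unadjusted t-test rejected a true null in 0.044-0.053 of runs against a nominal 0.0492 (Monte Carlo SE about 0.003).

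**5. Binary endpoints.** Mantel-Haenszel weights are n1k n0k / nk, the same information term as for fixed site effects. With 938 positives, the SE relative to the unstratified difference is 1.025-1.032 at ICC 0, 1.015-1.022 at 0.02, 1.000-1.007 at 0.05 and 0.974-0.981 at 0.10. Break-even is near 0.05. A second simulation, with an assumed mean rate of 40%, found equality at a between-site SD of 0.10, that is ICC = 0.10² / (0.40 × 0.60) = 0.042, which agrees.

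**The case against.** The strongest reply is that an unadjusted t-test is a legitimate, simple choice for a pragmatic trial and that the gain is close to nil at small ICCs. That stands as to size. The endpoint is a change from baseline, so a constant site or device offset cancels, which argues for a low ICC. The usual argument that ignoring strata makes a test conservative also has little force here, because the analysed subset is not balanced within site. With all of about 850 randomised participants analysed, the simulated error fell to about 0.041, but that is not this design.

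The second reply is that site may yet appear. The 9.6 list is worded as open, and a separate SAP is promised. This is fair for the trend models. It does not reach 9.4 and 9.5, which already name the methods.

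A reader might go further and infer three things that the documents do not support:

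- That blood pressure devices differ by site. Section 4.3 calls for digital devices, gives one model as an example and allows manual readings if needed; it does not say that sites differ.
- That varying decision support (7.8) adds site noise to both arms. Control results are returned after the 6-month visit, so before then the alerts reach only the Intervention arm. That would be variation in the treatment effect, which a random intercept does not remove.
- That the PGx comparison ignores its own stratification. Section 4.2 does not say that this allocation is stratified.

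Site-stratified risk differences might look natural for 9.5. They would pay off if event rates varied widely: at a between-site SD of 0.20 the unadjusted difference has 15-16% more variance. At low ICC they widen the intervals, and under 9.9 intervals are what is reported for secondary endpoints.

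**Conclusion.** The omission is real for the primary and secondary tests, and its consequence is minor. It forgoes about 0.3, 1 and 3 points of power at assumed site ICCs of 0.02, 0.05 and 0.10, and nothing at ICC 0. The documents give no ICC, so the true gain cannot be fixed within that range. The figures also treat the variance components as known.

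A reader might infer that leaving out the stratification factor makes the primary test invalid or the trial underpowered. Neither follows. The estimate is unbiased, simulated type I error is at its nominal level, and 844 completers with 80% power are correct for the test as planned. The case for change is that the random intercept, on these assumptions, does no worse than the t-test and uses data already held. For the binary endpoints the same reasoning is carried over; the gain from a random-intercept model was not computed separately.

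**What to change.** - **9.4:** estimate the difference in SBP change from a linear mixed model with arm and a random intercept for randomising site, tested at the 0.0492 level given in 9.7. Keep the t-test as a supportive result.
- **9.6:** add the same intercept to the trend and subgroup models.
- **9.5:** fit a model with a random site intercept to each binary endpoint and report a standardised risk difference with its 95% confidence interval.
- **Do not use** 46-60 fixed site terms or Mantel-Haenszel weights over sites.
- **PGx:** the same intercept is optional. State in 4.2 whether that allocation is stratified by site.

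If the sponsor prefers to keep the t-test as primary, one sentence saying why site is omitted would be enough. The cost is wording in the protocol and SAP, since site is already recorded. Because two interim analyses are accounted for, the choice should be made and dated by staff who have not seen outcomes by arm.
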